9.0 Study Estimands

9.1 Target Population

The target population consists of healthy subjects aged 18 to 45 years receiving one of three lots of VLA1553, which is a candidate vaccine intended to prevent CHIKV infections in the general population living in endemic regions, as well as to serve as a prophylactic measure for travelers to epidemic areas or areas at risk for an upcoming outbreak or ongoing endemic transmission. Subjects are screened for their CHIKV serostatus by ELISA at study entry; subjects who test positive for CHIKV as measured by ELISA assay are excluded from the PP analysis set. For the primary and secondary endpoint analysis the μ PRNT assay is used to determine neutralizing antibody titers.

9.2 Primary Endpoint

The primary immunogenicity endpoint is the geometric mean titer (GMT) of CHIKV-specific neutralizing antibodies as determined by μ PRNT assay on Day 29 post-vaccination in subjects who tested negative for CHIKV antibodies (as determined by ELISA) at baseline.

9.3 Secondary Endpoints

The following secondary immunogenicity and safety endpoints will be evaluated:

Immunogenicity

- Immune response as measured by CHIKV-specific neutralizing antibody titers on Day 8, Day 85 and Month 6 post-vaccination as determined by μ PRNT assay;
- Proportion of subjects with seroprotective levels (defined as [REDACTED] for baseline (μ PRNT) negative subjects) at Days 8, 29, 85 and Month 6 post-vaccination by μ PRNT assay;
- Proportion of subjects with seroconversion at Day 29 and Month 6 as determined by μ PRNT assay (seroconversion defined as CHIKV-specific neutralizing antibody titer of [REDACTED] for baseline (μ PRNT) negative subjects and [REDACTED] for baseline (μ PRNT) positive subjects);
- Fold increase of CHIKV-specific neutralizing antibody titers determined by μ PRNT assay at Day 8, 29, 85 and Month 6 post-vaccination as compared to baseline;
- Proportion of subjects reaching an at least 4-fold, 8-fold, 16-fold or 64-fold increase in CHIKV-specific neutralizing antibody titer compared to baseline as measured by μ PRNT assay.

Safety

- Frequency and severity of solicited injection site and systemic AEs within ten days post-vaccination;
- Frequency and severity of unsolicited AEs within 28 days postvaccination;
- Frequency and severity of any AE during the entire study period;
- Frequency and severity of any SAE during the entire study period;
- Frequency and severity of any AESI within 2 to 21 days post-vaccination.

The below table links the endpoints to the study objectives and specify the estimands of the study. Analysis sets are defined in section 9.4.

Table 9-1 Overview of study estimands

Objectives	Endpoints	Estimands	Study Part	Analysis Set

Objectives	Endpoints	Estimands	Study Part	Analysis Set
[REDACTED]	[REDACTED]	[REDACTED]	[REDACTED]	[REDACTED]

Objectives	Endpoints	Estimands	Study Part	Analysis Set

9.4 Analysis Sets

9.4.1 Safety Analysis Set

The safety analysis set (SAF) contains all subjects who entered into the study and received the vaccination. Subjects will be analyzed as treated.

9.4.2 Full Analysis Set

The full analysis set (FAS) contains all subjects who were randomized, received the vaccination and have evaluable immunogenicity data at the time point for the primary endpoint. Subjects will be analyzed as randomized.

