18.2 Datasets and Analysis Cohorts

The full analysis set contains all subjects who were randomized and received at least one vaccination. Subjects will be analyzed as randomized.

The safety analysis set contains all subjects who entered into the study and received at least one vaccination. Subjects will be analyzed as treated.

The per protocol (PP) analysis set contains all subjects who were baseline negative for CHIKV antibodies and have received the vaccination and have evaluable immunogenicity data at baseline and the time point for the primary endpoint without a major protocol violation. Examples that may lead to exclusion from the PP population are provided here, further criteria may be defined in the Statistical Analysis Plan (SAP):

- Subject has a known or suspected defect of the immune system that can be expected to influence the immune response to the vaccine, such as subjects with congenital or acquired immunodeficiency, including infection with HIV, status post organ transplantation or immuno-suppressive therapy within 4 weeks prior to Visit 1. Immuno-suppressive therapy is defined as administration of chronic (longer than 14 days) prednisone or equivalent ≥ 0.05 mg/kg/day within 4 weeks prior to study entry, radiation therapy or immunosuppressive cytotoxic drugs/ monoclonal antibodies in the previous 3 years; topical and inhaled steroids are allowed;

- Subject is positive for human immunodeficiency virus (HIV), hepatitis B surface antigen (HBsAg) or hepatitis C virus (HCV);
- Subject has received the wrong (not according to randomization) or no IMP.

These criteria for protocol violations are identified at the time of planning the study. However, during the course of the trial unforeseen events may occur or new scientific knowledge may become available, therefore final decisions on whether a protocol violation could impact on the immune response and thus lead to exclusion from the PP population will be made by the sponsor on a case by case basis in a blinded manner (prior to study unblinding). Sample testing issues may also lead to exclusion from the PP analysis for particular time points.

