6.1 Changes from Protocol

The Per Protocol analysis set uses different visit windows to define out of window results than outlined in the protocol schedule of events. This is in order to align the visit windows allowable in this analysis in line with the phase 1 study of this vaccine. The visit windows in the protocol are shown in section 11.2, whilst the windows for the exclusion from the Per Protocol analysis set are outlined in Section 9.5.2. Further, if an Unscheduled Visit falls into a Scheduled Visit window that either did not occur or occurred outside of the defined Scheduled Visit window, the Unscheduled Visit will be used in analyses in the place of the Scheduled Visit.

The definition of adverse event of special interest in section 11.7.5 has been updated per FDA feedback for clarification of the anatomical location with cutaneous pruritus. This is not yet reflected in Protocol version 3.0, which is the approved version at the time of SAP finalization.

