9.4.3 Per Protocol Analysis Set

The per protocol (PP) analysis set contains all subjects who were baseline negative for CHIKV antibodies as determined by ELISA assay, have received the vaccination and have evaluable immunogenicity data at baseline and the time point for the primary endpoint without a major protocol deviation. This analysis set will be the primary analysis set for immunogenicity analyses. Subjects will be analyzed in the PP analysis set according to the study arm they have been randomized to.

9.4.4

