13.4.3 Secondary Immunogenicity Analyses

The secondary immunogenicity analyses will be performed on the PP analysis set and repeated on the Full analysis set.

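### The SAP limits the full analysis set to subjects with an evaluable Day 29 titer, an unlisted change from the protocol that drops some subjects' titers at other visits from the secondary analyses in SAP 13.4.3

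*SAP*

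**What the plan says.** Protocol 18.2 requires no titer for the FAS: "The full analysis set contains all subjects who were randomized and received at least one vaccination", with subjects analysed as randomized. Under SAP 9.4.2 the same set "contains all subjects who were randomized, received the vaccination and have evaluable immunogenicity data at the time point for the primary endpoint". SAP 9.2 fixes that time point, since the primary endpoint is the GMT by μPRNT "assay on Day 29 post-vaccination in subjects who tested negative for CHIKV antibodies (as determined by ELISA) at baseline".

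PP members must, in SAP 9.4.3, "have evaluable immunogenicity data at baseline and the time point for the primary endpoint without a major protocol deviation". Protocol 18.2 sets the same condition for PP: "have evaluable immunogenicity data at baseline and the time point for the primary endpoint without a major protocol violation". The PP set is therefore not newly narrowed on this point; only the FAS is.

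SAP 13.4.3 names the sets for the secondary work: "The secondary immunogenicity analyses will be performed on the PP analysis set and repeated on the Full analysis set".

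SAP 6.1, the section for departures from the protocol, begins "The Per Protocol analysis set uses different visit windows to define out of window results than outlined in the protocol schedule of events". It goes on to the substitution of unscheduled visits and the wording of the adverse event of special interest. The FAS definition is not mentioned. The protocol lets the SAP add PP exclusion criteria (18.2) and choose which secondary analyses to repeat on the FAS (18.4.2.2). It does not pass the FAS definition itself to the SAP.

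**The concern.** The FAS is the only set in the protocol that would keep a vaccinated subject without a Day 29 result. Once it carries the Day 29 condition, that subject is in neither immunogenicity set, even with valid titers at other visits. The endpoints touched are GMT, GMFI, fold-increase categories and seroprotection at Day 8, Day 85 and Month 6, and seroconversion at Month 6.

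Two things are at stake. First, the FAS repeats at those visits describe only subjects who later, or earlier, produced a usable Day 29 sample. That is an event after randomization, so the repeats are no longer the broad comparison that a reader of the protocol would expect. Second, the missing-data safeguard in SAP 11.8 depends on counting subjects without a primary value, and both sets have removed those subjects beforehand.

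The documents foresee such subjects. Protocol 10.6 expects missed visits because of COVID-19. A footnote to protocol 13.5 lets a subject who was lost to follow-up return and complete the study. Protocol 18.2 expects sample-testing problems to remove particular time points.

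**Working it through.** **The plan's own figure.** The documents give 402 randomized (134 per lot), SD 0.32 on the log10 scale, two-sided 5%, overall power of about 90%, and losses of 10%, 5% and 2%. Evaluable per lot: 134 × 0.90 × 0.95 × 0.98 = 112.3. The margin is redacted, so the 90% cannot be strictly reproduced. With an assumed 1.5-fold margin and equal lots, the standard error of a pairwise difference is 0.32 × √(2/112) = 0.0428. Pairwise power is 2Φ(0.1761/0.0428 − 1.96) − 1 = 0.969, and its cube is 0.910. Simulating the three comparisons jointly gives 0.919. Assumed margins of 1.4- and 1.6-fold give about 0.68 and 0.99 by simulation. The stated size is thus coherent for a margin near 1.5-fold. It concerns the PP comparison, and the FAS definition does not enter it.

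**Who is in which set.** The definitions, applied to four kinds of vaccinated subject:

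| Subject | PP | FAS, protocol | FAS, SAP | Lost from SAP FAS repeats |
|---|---|---|---|---|
| Day 29 sample taken out of window | no (SAP 9.5.2) | yes | yes (SAP 9.5.2) | nothing |
| Leaves between Day 8 and Day 29, no substitute sample | no | yes | no | Day 8 |
| Misses Visit 3, then returns | no | yes | no | Day 8, Day 85, Month 6 |
| Attends Visit 3, titer not evaluable | no | yes | no | Day 8, Day 85, Month 6 |

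Under SAP 11.2 an unscheduled or early termination sample inside the Visit 3 window can stand in for Visit 3, which moves some subjects out of the last three rows.

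**Size.** The share without an evaluable Day 29 titer is not in the documents. Assumed range 2% to 10%:
- 0.02 × 402 = 8.0 subjects (0.02 × 134 = 2.7 per lot)
- 0.10 × 402 = 40.2 subjects (0.10 × 134 = 13.4 per lot)

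The top end treats the whole planned 10% drop-out as occurring before Day 29.

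**What the condition does at Day 29.** SAP 11.8 analyses observed values. A subject with no Day 29 titer contributes nothing to the Day 29 comparison under either FAS definition. The added condition therefore changes results only at the other visits.

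**The 5% rule.** SAP 11.8 calls for multiple imputation if more than 5% of values are missing for the primary analysis. Inside PP and inside the SAP FAS, the number missing at Day 29 is 0 by construction, so the share is 0%. With all 402 as denominator the threshold is 0.05 × 402 = 20.1, and 21 or more missing would trigger it. SAP 11.8 does not state the denominator. SAP 13.0 refers for details to 13.4.3.3, which is the section on seroconversion rate and gives none.

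**The case against.** The strongest reply is that no analysis required by the protocol changes. Protocol 18.4.2.2 puts the secondary immunogenicity analyses on PP, which already needs a Day 29 titer, and leaves any FAS repeats to the SAP. The one FAS repeat that the protocol fixes is the Day 29 comparison (18.4.1), which is the same on observed values under both definitions. This stands. The point is confined to secondary repeats that the SAP itself chose to run, and to the 5% rule.

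A reader might infer more, and the documents do not support it:
- *That the lot-consistency conclusion is at risk.* The primary analysis is on PP, and its population is unchanged. Nothing in the documents suggests that missing Visit 3 would differ by lot, since subjects and sites are blinded and all arms receive the same product.
- *That the Day 29 FAS repeat would otherwise have tested dependence on Visit 3 attendance.* An observed-case comparison cannot do that under either definition. The SAP FAS is also still broader than PP: it keeps ELISA-positive subjects, subjects with major deviations and out-of-window samples.
- *That seroconversion at Day 8 and Day 85 is affected.* SAP 9.3 and 13.4.3.3 plan it only at Day 29 and Month 6.
- *That every immunogenicity analysis is affected.* Table 9-1, SAP 9.4.4 and SAP 13.4.4 are not readable, so another set or analysis may exist. SAP 11.6.3 cites 9.4.4 for a set called sPP1 and links it to baseline μPRNT-negative subjects. That suggests a subset of PP, but does not settle it.
- *That the change was concealed.* The text shows an unlisted difference and no motive. The titers are also not lost altogether, since SAP 13.0 lists all collected data unless otherwise specified.

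SAP 13.0 also says that all available data are included whatever the subject's status, and protocol 13.5 says that data from withdrawn subjects will be used. Both sit awkwardly with the narrowed FAS, but neither overrides membership of an analysis set.

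**Conclusion.** The mismatch is real and undeclared. Under the readable text, a vaccinated subject without an evaluable Day 29 titer contributes to none of the secondary analyses in SAP 13.4.3, and the FAS repeats at Day 8, Day 85 and Month 6 are conditioned on a post-randomization event. The effect is a loss of supportive data; no bias between lots is shown.

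The count of 8 to 40 rests on the assumed 2% to 10%. Early drop-outs would probably make up most of it and lose Day 8 only. Day 85 and Month 6 losses need a subject who misses Visit 3 and returns, or an unevaluable Day 29 sample. The count falls further wherever an out-of-window, unscheduled or early termination sample supplies the Day 29 titer. The definitional point does not depend on the count.

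The 5% rule for multiple imputation cannot operate as written unless its denominator is all vaccinated subjects. The change is worth making because the condition gains nothing at Day 29 and removes valid titers elsewhere.

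**What to change.** In SAP 9.4.2, restore the protocol definition: all randomized and vaccinated subjects, analysed as randomized. State that each visit's analysis on the FAS uses every member with an evaluable titer at that visit. In SAP 11.8, name this FAS as the denominator for the 5% missing-data rule.

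If the sponsor prefers to keep the narrower set, SAP 6.1 should list and justify it, and a secondary analysis of all vaccinated subjects with a titer at the given visit should be added.

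The cost is one sentence and a changed population flag, plus the stated denominator for the 5% rule. Denominators will vary by visit, as SAP 13.4.3.2 already provides for the seroprotection rate. Sample size, power and the primary analysis stay as they are.

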9.4.3 Per Protocol Analysis Set

The per protocol (PP) analysis set contains all subjects who were baseline negative for CHIKV antibodies as determined by ELISA assay, have received the vaccination and have evaluable immunogenicity data at baseline and the time point for the primary endpoint without a major protocol deviation. This analysis set will be the primary analysis set for immunogenicity analyses. Subjects will be analyzed in the PP analysis set according to the study arm they have been randomized to.

9.4.4

9.5 Protocol Deviations

The study specific Protocol Deviation Guidance Document defines all important protocol deviations and all major protocol deviations.

Per PRA processes, protocol deviations data will be entered into the system of record (PSO). The study team and the Sponsor will conduct on-going reviews of the deviation data from PSO and the resulting set of evaluable subjects throughout the study, adjusting the deviation criteria as seems appropriate. The evaluable subjects set must be finalized at the post-freeze data review meeting (or earlier), prior to the database lock for each part of the study.

In addition, a separate table and listing of COVID-19 specific protocol deviations will be produced.

9.5.1 Classification of Protocol Deviations

Protocol deviations will be classified as major or minor protocol deviations based on their possible impact on the study results in a blind data review meeting prior to the database snapshots at each study part.

All protocol deviations will be tabulated, separated by minor and major deviations. Major deviations are those which will lead to the exclusion of subject from the PP analysis set. A tabulation of the number and percentage of protocol deviations by deviation type will be provided for each study part. A by-subject listing of all protocol deviations will be presented.

Final decisions on whether any protocol deviation could impact immune response and thus lead to the exclusion from the PP analysis set will be made by the sponsor on a case by case basis in a blinded manner (prior to study unblinding). Sample testing issues may also lead to the exclusion from the PP analysis for particular time points.

In order to help identify protocol deviations which would lead to exclusion from the PP analysis set, listings of concomitant medications, protocol deviations, and subject visits outside of time window will be produced at the time of database freeze activities.

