8.3 Blinding/Unblinding

The study is conducted in a double-blind manner. Investigators and all other study staff involved in study conduct, safety assessments and IMP handling (i.e. perform preparation of the study vaccine, maintain the drug accountability logs detailing the dates and quantities of IMP administered to each subject); study participants, biostatistician (except the unblinded independent reporting statistician involved in the Data Safety Monitoring Board [DSMB]), CRAs responsible for monitoring study data, IMP handling and verifying drug accountability, and lab staff will all be blinded to treatment allocation.

The randomization assignment is not to be revealed except in emergency cases in which unblinding is necessary for the clinical management of an SAE. In such events, the Investigator must either inform the Sponsor before breaking the blind or immediately after unblinding has been performed.

In case of emergency, the vaccine administered to the subjects can be revealed through the web-response system (IXRS).

The study will be unblinded for analysis purposes at the end of Part A (after all subjects have completed Visit 3/ Day 29), but sites and subjects will remain blinded until the end of study.

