10.0 Analyses Part A and Part B

10.1 Planned Analysis Timepoints

There are 2 planned data analyses on this study:

- Part A includes safety and immunogenicity data after all subjects have completed Visit 3 (Day 29).
- Part B includes safety and immunogenicity data after all subjects have completed Visit 5 (Month 6).

Individual study parts will be analyzed sequentially.

The study will be unblinded for Part A analysis once the final subject has completed Visit 3 and database lock for Part A has occurred (blind will be maintained for study sites and subjects). Unblinding of the study for Part B analysis will occur once the final subject has completed Visit 5 and database for Part B database has been locked.

The analyses to be done at each study part are specified within each section of the statistical methods part of this SAP.

For the Part A analysis, data up to and including Visit 3 (Day 29) or ET if earlier will be kept for all subjects, for the Part B analysis all data will be kept for all subjects. All AEs and concomitant medications with a start date up to and including the date of the cutoff visit for each subject will be included in the analysis. Any record with a start date prior to the cutoff which has a stop date recorded after the cutoff visit for the analysis will be classed as ongoing for the relevant study part.

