11.6.3 Seroconversion

Seroconversion is defined as a CHIKV-specific [REDACTED] for baseline μ PRNT negative subjects (PP, sPP1 for definition see section 9.4.3 and 9.4.4). Seroconversion for baseline μ PRNT positive subjects (included in PP) is defined as a [REDACTED] increase over baseline.

The seroconversion rate (SCR) is defined as the proportion of subjects meeting the criteria for seroconversion at the relevant study timepoint.

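### Per-protocol exclusions at Part B are to be decided blind and before unblinding, but the lots are opened after Part A and no visible text keeps the sponsor's reviewers blind

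*SAP*

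**What the plan says.** **When PP decisions are made.** SAP 9.5.1 classifies deviations as major or minor "in a blind data review meeting prior to the database snapshots at each study part". Final decisions on exclusion "will be made by the sponsor on a case by case basis in a blinded manner (prior to study unblinding"; protocol 18.2 has the same rule. SAP 9.5 adds that the set of evaluable subjects "must be finalized at the post-freeze data review meeting (or earlier), prior to the database lock for each part of the study", and that the study team and sponsor review deviations throughout the study, "adjusting the deviation criteria as seems appropriate". Protocol 20.6 likewise plans data review meetings for both the study-part analysis and the final analysis.

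**When the lots are opened.** SAP 8.3 states: "The study will be unblinded for analysis purposes at the end of Part A". SAP 10.1 puts this after "database lock for Part A has occurred (blind will be maintained for study sites and subjects". Protocol 18.5 keeps the blind for study sites only. SAP 10.1 also mentions a separate unblinding for Part B after the Part B lock. SAP 12.1 ties the Part A unblinding to the database freeze instead of the lock.

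**What the PP set is.** SAP 9.4.3 makes PP the primary set for immunogenicity and requires that subjects "have evaluable immunogenicity data at baseline and the time point for the primary endpoint without a major protocol deviation". SAP 11.6.3 refers to a further set ("PP, sPP1 for definition see section 9.4.3 and 9.4.4") whose definition is not public.

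**Where PP is used later.** SAP 13.4.3 runs the secondary comparisons on PP and repeats them on the FAS. Under SAP 12.1 the Part A&B report covers all immunogenicity data and goes to licensure. SAP 13.0 expects Part A time points to be summarized again in Part B.

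**The concern.** A blind review protects a PP analysis only if the people deciding exclusions do not know the treatment groups or the results by group. Here the decision-maker is the sponsor, the decisions are case by case, and the criteria may change during the study. Each subject has one lot assignment, made on Day 1, so once the codes are opened for Part A, the later unblinding in SAP 10.1 has nothing new to open.

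Major deviations after Day 29 are possible. Protocol 17.4.2 bars blood products, immunoglobulins and immunosuppressive therapy for the whole study. The visible PP definition sets no time limit on major deviations, and no visible text fixes Day 29 membership at the Part A lock. Read as written, a deviation on Day 100 could remove a subject from PP at every time point, decided by people who may have seen Day 29 results by lot.

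At stake are the Day 85 and Month 6 PP comparisons, and agreement between the Day 29 PP set decided blind and any Day 29 PP set presented in the licensure report.

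**Working it through.** The check is mainly one of order. The sequence in the documents is:

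1. Blind review, and evaluable set made final, before the Part A lock (SAP 9.5, 9.5.1).
2. Part A lock; lots opened; blind kept for sites and subjects (SAP 8.3, 10.1) or sites only (protocol 18.5).
3. Visits 4 and 5, Day 85 and Day 180.
4. A second blind review before the Part B snapshot and lock (SAP 9.5, 9.5.1).
5. Part B lock and a second unblinding (SAP 10.1).

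Step 4 follows step 2. A decision first made or revised at step 4 cannot precede study unblinding. It can still be made by someone who has not seen the codes, but no visible text provides for that.

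**Freeze and lock.** SAP 9.5 allows the evaluable set to be finalized at a meeting after the freeze. Under the SAP 12.1 trigger, the codes could be opened before that meeting. Under the SAP 10.1 trigger they could not.

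**Size, as an illustration only.** The plan gives no frequency for deviations after Day 29. Inputs from protocol 18.1: 134 per lot, SD 0.32 log10, losses of 10%, 5% and 2%.

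- Evaluable n per lot = 134 × (1 − 0.10 − 0.05 − 0.02) = 111 (112 if the losses are multiplied).
- The stated power of about 90% cannot be verified because the margin is redacted. With n = 111 and no true lot difference, simulated joint power is 67.7% at an assumed 1.4-fold margin, 91.5% at 1.5 and 98.5% at 1.6. The point here does not depend on this.
- SE of a lot difference = 0.32 × √(2/111) = 0.04295. The 95% half-width = 1.967 × 0.04295 = 0.0845 log10, a factor of 1.215.
- Removing k subjects regardless of titer shifts the lot mean by 0 on average, with SD 0.32 × √(k / (111 × (111 − k))).
- Removing k subjects who all lie d SDs on the same side shifts it by k × d × 0.32 / (111 − k).

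| k | d | SD of chance shift | Same-side shift | GMT factor (same-side) | Share of half-width | Same-side ÷ chance SD |
|---|---|---|---|---|---|---|
| 1 | 1 | 0.0029 | 0.0029 | 1.007 | 3% | 1.0 |
| 2 | 2 | 0.0041 | 0.0117 | 1.027 | 14% | 2.9 |
| 4 | 2 | 0.0059 | 0.0239 | 1.057 | 28% | 4.1 |

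The values of k and d are assumptions. So is carrying n = 111 and SD 0.32, which are planning figures for Day 29, over to Day 85 and Month 6.

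**The case against.** A reader might infer that the Part B review must be unblinded, so that the safeguard cannot work. The documents do not support that. SAP 8.3 opens the study for analysis purposes, which need not mean that everyone who classifies deviations receives lot codes. Protocol 12.4 lists sponsor and CRO staff as blinded and gives no end date. SAP 10.1 places a Part B unblinding after the Part B lock. One consistent reading is that analysis staff see the codes after Part A while the deviation reviewers stay blind. This stands as a possibility, but neither document provides for such a group.

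The room for discretion may also be narrow. The Protocol Deviation Guidance Document, which was not supplied, defines the major deviations and may already hold fixed rules. Table 9-1 and SAP 9.4.4 are redacted, so it cannot be established that Day 29 membership is re-derived at Part B. The exclusion examples in protocol 18.2 concern eligibility or dosing. Out-of-window samples at Visits 4 and 5 follow a fixed rule and count as minor (SAP 9.5.2). Protocol 17.4.2 calls a barred treatment a protocol deviation, not a major one. Sites and central laboratories are listed as blinded, so deviations and sample problems are recorded by blinded people. All of this reduces the exposure. It does not remove it, because SAP 9.5 lets the criteria be adjusted and SAP 9.5.1 leaves case-by-case and sample-testing exclusions to judgment.

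The last row of the table is extreme. The plan allows 5% major deviations, or 0.05 × 134 = 6.7 per lot, and four late removals would be about 60% of that.

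**Conclusion.** The conflict in timing is real and limited. For deviations first classified or reclassified at Part B, the condition of deciding before study unblinding cannot be met literally, and no visible text guarantees that the sponsor's reviewers are still blind.

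A reader might also infer that the primary lot-consistency result is at risk. It is not under SAP 10.1: the Part A set is final before the lock and the codes are opened after it. The freeze wording in SAP 12.1 conflicts with that order, but the SAP 9.5.1 requirement to decide before unblinding still applies, so this is an inconsistency to correct and not evidence of an unblinded primary set.

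What remains exposed is the Day 85 and Month 6 PP comparisons, plus any Day 29 PP result presented again in the Part A&B report. The later comparisons are secondary, have no visible acceptance margin and are repeated on the FAS. Reasons for exclusion are listed (SAP 13.1), so removals can be traced, although tracing does not make a decision blind. The magnitude is unknown and probably small; the illustrated range is 0.7% to 5.7% of one lot's GMT under assumed one-sided removals. The conclusion rests on the visible text and would weaken if unseen documents name a shielded review group or freeze Day 29 membership.

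**What to change.** In SAP 9.5, state that:

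1. PP membership for Day 8 and Day 29 is fixed at the Part A lock and used unchanged in the Part A&B report. A deviation that first occurs after the Visit 3 sample can remove only later samples.
2. Deviations arising after Part A are classified and documented before the Part B lock, either by named existing sponsor or CRO staff with no access to lot codes or by-lot results, or by rules fixed before the Part A unblinding. Unblinded staff may not change the criteria.

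In SAP 12.1:

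3. Change the Part A unblinding trigger from database freeze to database lock, to match SAP 10.1.

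The cost is one SAP paragraph and one changed word, with no new data or staff. The downside is that a few existing staff must stay blinded to lot codes and Part A by-lot results until the Part B lock.
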